8.1 Effectiveness Assessments

8.1.1 GINA Guideline-Recommended Treatment

The primary endpoint is the proportion of patients with an ICS-based maintenance and/or reliever treatment, which is indicated by whether or not the treatment option includes ICS-containing medication.

The pulmonologist will record the current treatment (reliever and controller) at this visit.

8.1.2 GINA Guideline-Preferred Treatments

One secondary endpoint is the proportion of patients on the treatment of ICS-formoterol as reliever, without concomitant SABA.

8.1.3 Asthma Related Treatment Pattern

Asthma related treatment patterns will be evaluated by treatment distribution at baseline and at weeks of 12, 24, 36, and 48, e.g., ICS-containing medications, ICS-LABA, ICS-formoterol, oral corticosteroids, leukotriene receptor antagonists, theophylline, Traditional Chinese Medicine and combination.

8.1.4 Hospitalization due to Exacerbations

Hospitalization due to asthma exacerbation is defined as deterioration of asthma that requires a medical intervention as described below:

- A hospital admission.

And

- Prescription with one or more of the following medications to treat asthma symptoms worsening:
 - Systemic corticosteroids
 - Nebulized SABA or SAMA or SABA/SAMA combination
 - Theophylline (injection)
 - New prescription of ICS or increased dose of ICS for at least 3 days (nebulized or inhaled)

8.1.5 Severe Exacerbations

A severe exacerbation defined as worsening asthma leading to the prescription of systemic glucocorticoid treatment for at least 3 days or hospitalization or an ED visit.

8.1.6 Patient Reported Outcomes (PROs)

During the study, two PRO questionnaires (ACQ-5 and AQLQ(S)+12) will be administered to participants at site at weeks of -12 (baseline), 0, 12, 24, 36, and 48. The participants should be given adequate time to complete all items in a quiet environment, ideally prior to their meeting with the pulmonologists. PROs will be completed by participants themselves independently prior to other study procedures. Site personnel should check whether participants completed the questionnaires at the appropriate visit. See Appendix C.

8.1.6.1 Asthma Control Questionnaire-5 (ACQ-5)

Change from baseline in the proportion of patients with well-controlled asthma rate evaluated by ACQ-5, change from baseline in ACQ-5 score and distribution of asthma control status evaluated by ACQ-5 will be evaluated.

The ACQ-5 is a shortened version of the full 7-item ACQ (Juniper et al 1999) that assesses asthma symptoms (night-time awakening, symptoms on awakening, activity limitation, shortness of breath, and wheezing) but omits the FEV1 measurement and SABA use from the original ACQ assessment. Patients are asked to recall how their asthma has been during the previous week by responding to 5 symptom questions. Questions are weighted equally and scored from 0 (totally controlled) to 6 (severely uncontrolled). The mean ACQ-5 score is the mean of the responses. Mean scores of ≤ 0.75 indicate well controlled asthma, scores between >0.75 and <1.5 indicate partly controlled asthma, and a score ≥ 1.5 indicates not well controlled asthma (Juniper et al 2006). Individual changes of ≥ 0.5 are considered to be clinically meaningful (Juniper et al 2005).

The ACQ-5 will be administered to participants at baseline (week -12), week 0, week 12, week 24, week 36, and week 48 and entered into the EDC. ACQ-5 must be completed by the participant at each visit (weeks of 0, 12, 24, 36, and 48) prior to any other study procedure.

8.1.6.2 Asthma Quality of Life Questionnaire (+12) AQLQ(S)+12

The AQLQ(S)+12 (Juniper et al 1992, Juniper et al 2005) is a PRO that measures the health-related quality of life experienced by asthma patients 12 years old and above. The questionnaire comprises 32 items in 4 separate domains (symptoms, activity limitations, emotional function, and environmental stimuli). Patients are asked to recall their experiences during the previous 2 weeks before each visit and to score each of the questions on a 7-point scale ranging from 7 (no impairment) to 1 (severe impairment). The overall score is calculated as the mean response to all questions. The 4 individual domain scores are the means of the responses to the questions in each of the domains. Individual AQLQ(s)+12 total or domain score changes of ≥ 0.5 are considered clinically meaningful (Juniper et al 1994).

A validated Chinese version of AQLQ(S) +12 will be used. AQLQ(S)+12 must be completed by the subject at weeks of 0, 24 and 48, after the ACQ-5 evaluation, prior to other study procedures.

Participants are asked to recall their experiences during the previous 2 weeks before each visit and to score each of the questions on a 7-point scale ranging from 7 (no impairment) to 1 (severe impairment). The total score is calculated as the mean response to all questions. The 4 individual domain scores are the means of the responses to the questions in each of the domains. Individual AQLQ(s)+12 total or domain score changes of ≥ 0.5 are considered clinically meaningful (Juniper et al 1994).

8.1.6.3 Patient Evaluation on Guideline Implementation KPIs

Guideline implementation performance will be assessed based on pre-defined key performance indicator (KPI). After seeing their pulmonologists, participating patients will be asked the following 5 KPI questions:

- Whether or not your pulmonologist or specialist nurse has assessed your symptom control over the past 4 weeks?
- Whether or not your pulmonologist or specialist nurse has watched you using your inhaler and educate the technique?
- Whether or not your pulmonologist has a discussion about why you need a long-term medication adherence?
- Whether or not your pulmonologist has developed or reviewed the written asthma action plan?
- Whether or not the pulmonologist has reduced the dosage of asthma treatment? If yes, whether or not you had a PFT before dosage reduction?

8.1.6.4 Patient's expectation for asthma treatment Questionnaire

Measures of patient's expectation were obtained from the following items that were part of the enrolment interview. Part patients were asked the open-ended question: “What do you expect from your asthma treatment?” these answers were collected, and high frequency sentences are adopted as options. (Appendix C3)

An established multicomponent model to examine possible variables related to the expectation of being cured, which is also integrated in this questionnaire ([Mancuso CA, 2003](#))

8.1.6.5 Disease Knowledge Questionnaire for Asthma Patients

The questionnaire was designed from ‘The Validity and Reliability of an Asthma Knowledge Questionnaire Used in the Evaluation of a Group Asthma Education Self-Management Program for Adults with asthma’ covers etiology, pathophysiology, drug and disease severity assessment, symptom management (including reducing triggers and exercise). Each question is answered "correctly", "wrongly" or "unsure", the scoring method is positive questions, and the score is correct, and the score is wrong. 1 point for correct judgment and full is 25 points, no points for wrong judgment and unsure choice. ([Allen, 1998](#)) According to a local study, based on this questionnaire, it was optimized to 25 items to evaluate the effect of asthma education ([Tian, 2014](#)). (Appendix C4)

8.1.6.6 Patient Self-Assessment of Asthma Severity

A question is asked respondents to self-report their asthma severity: “What is the level of severity of your asthma?”. The response choices for questions were “mild”, “moderate”, or “severe”. This question is used to define asthma severity based on self-reported severity. ([Ding, 2017](#))

8.1.6.7 Patient Adherence Assessment

Adherence assessment include PDC(proportion of days covered), MPR(medication possession ratio)([Carlyne M.2022](#))and based on Medication Adherence Report Scale for Asthma, the self-assessment of adherence is developed, more details in Appendix C6, C7.

MARS-A scale consists of 10 items, which are self-reported, and each question is scored on a scale of 1 to 5. The higher the score, the better the adherence. In the end, the average score of 10 questions was taken, and a score of 4.5 or above indicated good adherence. Items have both general and asthma-specific questions. The problem statement is in a negative way. ([Jessica 19L Cohen 2009 , Yu 2014](#)) and analysis of the reasons for non-compliance with doctor's orders, the influencing factors of compliance are based on a regional compliance study design in China ([Shi, 2019](#))

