6.1.1 The Scientific Content of Guideline Education

The education content is based on GINA 2021 recommendations, including the following major components:

- Asthma disease knowledge
- Asthma diagnosis and assessment
- GINA 2021 recommended evidence-based asthma treatment, e.g., low-dose ICS-formoterol as preferred reliver and the scientific rationale. A GINA 2021 based treatment pathway will be suggested to be followed by participating pulmonologists.
- How to educate and manage patients, e.g., written action plan, shared goals development, rationale for medication adherence, difference between reliever and controller, prevention of symptoms and flare-ups, how to recognize worsening asthma and what actions to take, etc.

The scientific steering committee (see section 6.1.2.4) will ensure the education and training materials are scientifically and clinically appropriate and fit-for-purpose.

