18. If you have a cold or flu, you should increase your asthma medication dosage (T)
19. Oral medications work just as fast as inhaled medications (F)
20. Because inhaled drugs work locally in the respiratory tract, they have fewer side effects than oral drugs. (T)
21. Asthma-relieving drugs (such as Ventolin or Terbutaline) do not work well if they are always used (T)

Condition monitoring

22. If the asthma does not have an attack, it is not necessary to visit the outpatient clinic regularly (F)
23. Regular pulmonary function tests can monitor changes in the condition (T)
24. Monitoring with a peak flow meter can provide an early indication of asthma exacerbation (T)
25. Keeping an asthma diary every day will help you know well your own condition (T)

Total 16T 9F

C 5 Patient Self-Assessment of Asthma Severity

Patient Self-Assessment of Asthma Severity

How severity level do you think your asthma is? (according to personal understanding)

A mild

B Moderate

C severe

C 6 Patient Adherence Assessment at baseline

Patient Adherence Assessment at baseline

1. Has your doctor told you that your asthma medication is for long-term use?

Yes

no

(Answer "yes", skip to 2)

2. Are the drugs you are currently using is inhaler?

Yes

no

(Answer "yes", skip to 3)

3. Please try to recall your usual medication situation. If you always agree with the following descriptions, please check "Level 1" after the corresponding description. If you do not do this at all, please check "5" level", and so on.

(1-always, 2-often, 3-sometimes, 4-rarely, 5-never)

Answer the following 10 questions

1. I only use this medicine when I need it
2. I only use it when I feel breathless
3. I decided to miss out a dose
4. I try to avoid using it
5. I forget to take it
6. I alter the dose
7. I stop taking it for a while
8. I use it as a reserve if other treatment doesn't work
9. I use it before doing something which might make me breathless
10. I take it less than instructed

4. When you were enrolled in the group, you did not take the medicine as prescribed by the doctor. What was the reason? (Multiple choice)

1. Forgetting medication, difficult to adhere to for a long time
2. The device is troublesome to use and inconvenient to carry
3. Unreasonable drug prices and unaffordable economy

4. It is troublesome to dispense the medicine, and the medicine cannot be dispensed continuously
5. Reluctance to use inhalation for a long time

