4.2.3.10 Exploratory Endpoint-10

4.2.3.11 Exploratory Endpoint-11

4.2.3.12 Exploratory Endpoint-12

4.2.3.13 Exploratory endpoint-13

4.2.4 Subgroup analyses

Subgroup analyses as below will be performed as appropriate for the primary endpoint, selected secondary endpoints and exploratory endpoints. Any subjects with a missing value for the defined subgroup will be excluded from the analysis of that subgroup. The subgroups to be explored may include as needed:

- Age by category: >65 years, ≥ 18 to ≤ 65 years, <18 years old
- Age of onset: <20 years old, <40 years old, ≥ 40 years old
- Phenotype of asthma: allergic or non-allergic
- Hospital Tier: Tier 2, Tier 3
- Job: related to asthma, no-related to asthma (occupational exposure Y or N)
- Nicotine usage frequency (current, former, never)
- Sex (Male, Female)

- BMI ($\geq 24 \text{ kg/m}^2$, $< 24 \text{ kg/m}^2$)
- Education level (elementary school and below, high school, university degree and postgraduate)
- Questionnaire with response and non-response subjects (if the subject performed ACQ and AQLQ at Visit 5 and had any questionnaire performed in each visit, the subject is defined as responder; otherwise, the subject is a non-response subject)
- Adherence (Good adherence or not)
- Patient expectation of asthma treatment
- Asthma severity class: Mild, Moderate, Severe (based on Patient Self-Assessment of Asthma Severity)
- Symptoms: Symptoms less than twice a month; Symptoms twice a month or more, but less than 4-5 days a week; Symptoms most days, or waking with asthma once a week or more; Daily symptoms, or waking with asthma once a week or more, and low lung function
- Hospital Type: PCCM, non-PCCM
- Geographic region: North, South
- ICS containing change: with-to-with, with-to-without, without-to-with, without-to-without ICS containing (From ICS containing to ICS containing, from ICS containing to no-ICS-containing, from no-ICS-containing to ICS-containing, from no-ICS containing to no-ICS-containing.)
- ICS-formoterol as reliever: with-to-with, with-to-without, without-to-with, without-to-without ICS-formoterol as reliever (From ICS-formoterol as reliever to ICS-formoterol as reliever, from ICS-formoterol as reliever to no-ICS-formoterol as reliever, from no-ICS-formoterol as reliever to ICS-formoterol as reliever, from no-ICS-formoterol as reliever to no-ICS-formoterol as reliever.)
- Participants complete status: Missing at Week 24, not Missing at Week 24.

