5 INTERIM ANALYSIS

There will be two interim analyses, first interim analyses will mainly focus on the baseline when all subjects enrolled and finish baseline assessment, and the other will happen when all subjects complete week 12 visit.

First interim analysis includes the following parts:

1. Subject disposition
2. Demographics
3. Substance use – nicotine
4. Asthma history
5. Historical asthma exacerbation
6. Prior and concomitant medications – asthma/asthma related comorbidities
7. Prescribed medication – asthma
8. ICS-based maintenance and/or reliever treatment
9. ACQ-5 average scores
10. Distribution of ACQ-5 average scores (Well controlled/Partly controlled/Not well-controlled) and its subgroup listed in Section 4.2.3.12
11. ICS-formoterol as reliever
12. Asthma treatment patterns
13. Numbers of severe asthma exacerbation
 - a. With ICS containing vs. without ICS containing
 - b. Good adherence vs. not
14. Health-related quality of life evaluated by Asthma Quality of Life Questionnaire for 12 years and older (AQLQ(S)+12) score
15. MARS-A average score
16. Hematology

17. Blood Gas
18. IgE
19. FeNO
20. Pulmonary Function Test (PFT)
21. Pulmonary Function Test-Post-BDT (PFT)

Second interim analysis includes the following parts:

1. Subject disposition
2. Demographics
3. Substance use – nicotine
4. Asthma history
5. Historical asthma exacerbation
6. Prior and concomitant medications – asthma/asthma related comorbidities
7. Prescribed medication – asthma
8. ICS-based maintenance and/or reliever treatment
9. ACQ-5 average scores
10. Distribution of ACQ-5 average scores (Well controlled/Partly controlled/Not well-controlled) and its subgroup listed in Section 4.2.3.12
11. ICS-formoterol as reliever
12. Asthma treatment patterns
13. Patient evaluation on whose pulmonologists (whether their pulmonologists develop or review the written asthma action plan and watch the patient using their inhaler, checking their technique)
14. Numbers of severe asthma exacerbation
 - a. With ICS containing vs. without ICS containing
 - b. Good adherence vs. not

15. Health-related quality of life evaluated by Asthma Quality of Life Questionnaire for 12 years and older (AQLQ(S)+12) score
16. MARS-A average score
17. Inhaler skill score of subjects
18. Asthma knowledge score of subjects
19. Patient expectations of asthma treatment
20. Asthma knowledge questionnaire score of investigators
21. Adverse event
22. Hematology
23. IgE
24. FeNO
25. Pulmonary Function Test (PFT)

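### The MARS-A cut-off of 4.5 can class a patient who correctly follows an as-needed-only ICS-formoterol prescription as not having good adherence, so the label is not comparable across regimens

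*Protocol*

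**What the plan says.** Protocol 8.1.6.7 scores MARS-A as a plain mean ("the average score of 10 questions was taken") and sets the threshold: "a score of 4.5 or above indicated good adherence". The response coding in Protocol Appendix C6 and C7 is "1-always, 2-often, 3-sometimes, 4-rarely, 5-never", and every item is worded so that 'always' counts against the patient. Item 1 is "I only use this medicine when I need it" and item 2 is "I only use it when I feel breathless". Item 9 asks about use ahead of something that might bring on breathlessness.

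The programme's teaching content (Protocol 6.1.1) includes "low-dose ICS-formoterol as preferred reliver and the scientific rationale". The primary endpoint counts ICS-based treatment whether it is maintenance, reliever or both (Protocol section 3 and 8.1.1). A secondary endpoint counts ICS-formoterol as reliever without concomitant SABA (Protocol 8.1.2).

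The label is used in two visible places. SAP 4.2.4 has the subgroup entry "Adherence (Good adherence or not". SAP section 5 lists severe exacerbations by "Good adherence vs. not" at both interim analyses.

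**The concern.** Items 1 and 2 suit an inhaler meant to be taken every day, where use only when needed is a failure to follow the prescription. For a patient whose whole prescription is as-needed ICS-formoterol, the same behaviour is what was prescribed. That patient can be a success on the primary endpoint and on the ICS-formoterol reliever endpoint, yet be placed in the group without good adherence.

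The lead-in questions on the forms do not settle this. C6 and C7 ask whether the doctor described the medication as long-term and whether it is an inhaler. They do not ask whether it is taken on a schedule or as needed, and they give no route for 'no'. In C7, a patient who says that the doctor's advice was followed goes on to the same ten items, so one form can record both advice followed and adherence not good. No visible text says which inhaler 'this medicine' means for a patient who has two.

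What is at stake is the meaning of the not-good group. If it contains correctly treated as-needed-only patients, a comparison of exacerbations by adherence is partly a comparison of regimens.

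**Working it through.** **Inputs.** Ten items, unweighted mean, cut-off 4.5 (Protocol 8.1.6.7); always = 1 to never = 5 (Appendix C6 and C7). The cut-off is adopted, not calculated, so there is no plan figure to reproduce.

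**Room below the maximum.** The maximum total is 10 × 5 = 50. The cut-off needs 10 × 4.5 = 45, so at most 5 points may be lost. Each 'always' loses 4.

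**Item patterns, all unnamed items at 5.**

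| Answers | Mean | At least 4.5? |
|---|---|---|
| Item 1 always | (1 + 9×5)/10 = 4.6 | yes |
| Item 1 always, item 2 rarely | (1 + 4 + 8×5)/10 = 4.5 | yes |
| Item 1 often, item 2 sometimes | (2 + 3 + 8×5)/10 = 4.5 | yes |
| Item 1 always, item 2 sometimes | (1 + 3 + 8×5)/10 = 4.4 | no |
| Items 1 and 2 often | (2 + 2 + 8×5)/10 = 4.4 | no |
| Items 1 and 2 always | (1 + 1 + 8×5)/10 = 4.2 | no |
| Items 1, 2 and 9 always | (3×1 + 7×5)/10 = 3.8 | no |
| Items 1 and 2 never (answering about a maintenance inhaler) | 50/10 = 5.0 | yes |

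With item 1 at 'always' and items 2 and 9 free, only one further point may be lost. That leaves 3 of the 5 × 5 = 25 combinations: 5/5, 4/5 and 5/4.

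**Direction over time.** The documents give no share of as-needed-only patients, so the mixes below are assumptions. As-needed-only users of any inhaler are taken never to reach 4.5, and a fraction g of maintenance users does. The good-adherence rate is then (maintenance share) × g, with g = 50% unless stated. Mixes 1 to 3 start from 60% SABA-only and 40% maintenance; only the 40% on ICS is a planning figure (Protocol 9.2).

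| Assumed change | Before | After |
|---|---|---|
| 1. 5 points from SABA-only to as-needed ICS-formoterol | 0.40×0.5 = 20.0% | 0.40×0.5 = 20.0% |
| 2. 5 points from SABA-only to maintenance | 20.0% | 0.45×0.5 = 22.5% |
| 3. 10 points to as-needed ICS-formoterol and 10 to maintenance | 20.0% | 0.50×0.5 = 25.0% |
| 4. Start 20% SABA-only, 80% maintenance; 10 points from each to as-needed ICS-formoterol | 0.80×0.5 = 40.0% | 0.70×0.5 = 35.0% |
| 5. As-needed-only rises from 5% to 25%, displacing maintenance | 0.95×0.5 = 47.5% | 0.75×0.5 = 37.5% |
| 6. As 5, with g rising to 65% | 47.5% | 0.75×0.65 = 48.8% |

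The rate can stay level, rise or fall.

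**The case against.** A reader might infer that measured good adherence must fall as the programme succeeds. The documents do not support that. Success is any ICS-containing treatment, maintenance included. Patients using SABA alone as needed lose the same points on items 1 and 2, so moving them to as-needed ICS-formoterol changes nothing and moving them to maintenance raises the rate. A fall needs as-needed-only use to displace maintenance without an offsetting gain in adherence. Training at each site starts only after its last patient is enrolled, so a programme effect cannot distort the baseline data on which the first interim focuses. Misclassification by regimen can still be present there.

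Other objections narrow the point. Teaching ICS-formoterol as the preferred reliever is not the same as prescribing it alone. Protocol 2.1 speaks of ICS-containing controller treatment for all adults and adolescents. The as-needed-only regimen appears as one step 1 answer option in the investigator test (Appendix D), with no key shown. The long-term-use question may also keep some as-needed patients from being scored. These points limit how many patients are affected, but none removes the problem for those who are scored.

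The threshold comes with cited sources, and adopting it unchanged is a defensible start. Protocol 8.1.6.7 also names two refill-based measures, but the only visible threshold for good adherence is the MARS-A one. The exploratory endpoint text (Protocol 9.4.2.3, SAP 4.2.3) is blacked out, so regimen-specific handling there cannot be checked and should not be called absent.

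**Conclusion.** The concern holds in a limited form. Under the visible rule, an as-needed-only patient who follows the prescription and answers 'always' to items 1 and 2 is capped at 4.2 (3.8 with item 9) and is classed as not having good adherence. This depends on how the patient answers: 'always' on item 1 alone leaves 4.6. The label is therefore not comparable between regimens, or over time if the mix of regimens changes. The direction and size of any shift are undetermined.

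This assumes that the SAP's good-adherence label means the protocol's MARS-A threshold and that as-needed-only patients complete the scale. If they also have fewer exacerbations, which the documents do not state, their presence in the not-good group would understate the contrast between adherent and truly non-adherent patients.

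The consequence is minor. No primary or secondary endpoint is built on the label, the subgroup is declared exploratory, and the interim splits carry no stated decision rule. It is worth correcting because the correction is cheap.

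**What to change.** In the SAP, apply the 4.5 cut-off, the adherence subgroup and the good/not-good exacerbation comparisons only to patients whose recorded treatment at that visit includes scheduled maintenance (controller) treatment. Report as-needed-only patients as a separate category, neither good nor not good. Name the record used to classify them: Protocol 8.1.1 has the pulmonologist record reliever and controller at the visit. If the blacked-out exploratory text already contains such a rule, a cross-reference from SAP 4.2.4 and section 5 is enough.

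The change needs a few lines of SAP text and no new data. The price is a smaller group in the adherence tables and one more category to report. No treatment or other clinical rule changes.
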